 - **Setting:** 4 major trauma networks within the West Midlands, Yorkshire, South Western and London Ambulance Services.
 - **Study design:** Single gate diagnostic accuracy cohort study with a census sample of reference standard positive major trauma cases; and random sample of reference standard negative cases without major trauma.
 - **Study population:** Patients attended by ambulance following injury. Sub-group analyses of children (<16 years) and elderly patients (≥65 years).
 - Study sample:
 - Reference standard positive cases: Census sample of consecutive cases meeting MATTS reference standard /secondary reference standards, identified through augmented TARN processes.
 - *Reference standard negative cases:* Random sample of cases presenting to EMS with injury. Appropriate patients identified using injury related working impression codes, use of major trauma interventions, hospital trauma team pre-alerts, and call priority.

Data collection:

- Ambulance service data: fixed fields used as recorded in EPR. Free text fields coded by research paramedics blinded to reference standard.
- TARN data: Fixed fields as recorded in TARN database. Additional MATTS required data fields completed by TARN data coordinators/research paramedics as required.
- Data linkage: Research paramedics to review all reference standard positive cases and manually determine a definitive EMS identifier for deterministic linkage. Non-linked cases assumed to be reference standard negative.
- Data governance: The proposed study design change does not affect data flows; and CAG and ethics approvals should be unaffected.
- Index tests: Existing and expert consensus-derived major trauma triage tools scored according to observed pre-hospital variables by blinded research paramedics. Identifiable data and reference standard classification withheld from research paramedics during triage tool coding.
- Reference standard: Patients with the potential to benefit from MTC care previously defined by independent expert consensus (clinicians, stakeholders) and Patient and Public Involvement (PPI) consultation. Secondary reference standards of Injury Severity Score (ISS) >15 and US consensus definition. Major trauma cases identified through augmented TARN case ascertainment process, supported by MATTS research paramedics.
- **Outcomes:** Sensitivity/specificity (corresponding to 1-Under/over-triage rates).

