 - Reference standard positive cases: Census sample of consecutive cases meeting MATTS reference standard /secondary reference standards, identified through augmented TARN processes.

- Reference standard negative cases: Random sample of cases presenting to EMS with injury. Appropriate patients identified using injury related working impression codes, use of major trauma interventions, hospital trauma team pre-alerts, and call priority.
- Outcomes: Under/over-triage rates based on actual patient destinations and observed hospital pre-alerts.
- Data collection: Linkage of pre-hospital and hospital variables using prospective EMS and augmented TARN data.
- Sample size: EMS/TARN data suggests approximately 300 major trauma cases (ISS>15) per 6 months per trauma network. Assuming, based on ASCOT criteria, a triage tool requires sensitivity of 95%, the total of 1,200 major trauma cases would give a 95% confidence interval coverage of ±1.0% for the under-triage rate. EMS data suggests approximately 37,500 patients presenting with injury over 6 months per trauma network (total 150,000 across all 4 of the participating trauma networks). Assuming a target specificity of 70% as per ASCOT guidance, coding 3000 reference standard negative cases (sampling fraction of 2%) would give a 95%CI coverage of ±1.5% for specificity.
- Evaluation of acceptability and usability to patients, ambulance services, and other important stakeholders using mixed-methods
- Cost-effectiveness of alternative triage tools using decision analytical modelling.

Project timetable: 31 month funded 3-phase research programme.

- Phase 1 Development Work: Permissions and set up, systematic review, retrospective cohort study, clinician focus groups, decision analytical modelling, and expert consensus process (10m). Conducted prior to the Phase 2 validation and Phase 3 implementation studies primarily considered in the current protocol.
- Phase 2 Validation Study: Prospective data collection, linkage and analysis (8m);
- Phase 3 Service Evaluation: Triage tool implementation, mixed methods assessment of performance, acceptability and usability (7m);
- Close-out: cost-effectiveness modelling, analysis and write-up (6m).

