5.1 Validation Study

The Phase Two validation study is a prospective diagnostic accuracy cohort study. Major trauma triage tools identified and developed in Phase One will be validated using linked EMS and hospital data.

Setting and study population

The MATTS Phase Two validation source population will be a single major trauma network, within each participating ambulance service:

- West Midlands Ambulance Service (WMAS)
- Yorkshire Ambulance Service (YAS)
- London Ambulance Service (LAS)
- South Western Ambulance Service (SWAST)

Patients of any age will be included in analyses if attended following injury by EMS within a participating regional Trauma Network. Patients transported to participating hospitals from non-study EMS, transported to out-of-area hospitals by participating EMS, or where record linkage would not be possible will be excluded. Patients from mass-casualty major incidents will also be excluded as special, non-standard, triage strategies are necessary in these scenarios. A census sample of consecutive patients will be enrolled over 4 months from WMAS, YAS, and SWAST in Phase Two; to allow achievable data collection from paper based records a representative cohort will be enrolled from the participating LAS Major Trauma Network using random sampling.

Collaborating EMS include a diverse range of settings and it will therefore be possible to investigate the influence of differing contexts on triage tool performance, for example, varying rates of blunt versus penetrating trauma and shorter versus longer transport times.

Identification of injured patients

Patients presenting with injury to ambulance services where major trauma could be expected will be identified from YAS, WMAS and SWAST electronic patient administrative systems, including computer aided dispatch records and patient report forms. Diagnostic codes for injury will be used where possible, with additional electronic searching of free text filters. Manual review of patient records will be performed in equivocal cases. LAS uses paper PRFs which are scanned with computerised extraction of basic demographic and clinical data. Identification of patients with injury in LAS will be performed by electronic searching for injury codes supplemented by direct review of paper records. To evaluate the completeness of patient identification a sub-sample of unfiltered records will be scrutinised by hand to detect the proportion of any missed cases.

Consent procedures

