Patient identifiable data (names, date of birth, and contact details) will not be collected or stored. The study manager, data managers, CI, research paramedics and administrators will have access to anonymised data on the study database, through the use of usernames and encrypted passwords. The Sponsor will permit monitoring and audits by the relevant authorities, including the Research Ethics Committee. The CI will also allow monitoring and audits by these bodies and the Sponsor, providing direct access to source data and all study documentation. All data will be collected and retained in accordance with the Data Protection Act 1998, European Union General Data Protection Regulations (GDPR) 2018, HRA Confidentiality Approval Group (CAG) approvals, and University of Sheffield CTRU SOPs. Output for analysis will be generated in a format and at intervals to be agreed between Sheffield CTRU and the CI.

Sample size calculation

TARN/EMS data suggests approximately 200 major trauma cases (ISS>15) per 4 months per trauma network. Assuming a target sensitivity of 95% as per American College of Surgeons Committee on Trauma (ASCOT) guidance, the total of 800 reference standard positive cases would give a 95% confidence interval coverage of 2% for sensitivity. EMS data suggests approximately 25,000 patients presenting with injury over 4 months per trauma network (total 100,000 across all 4 of the participating trauma networks). Assuming a target specificity of 70% as per ASCOT guidance, coding 2000 reference standard negative cases (sampling fraction of 2%) would give a 95%CI coverage of 2% for specificity. The total sample size of 2,800 cases would equate to an approximate total of 700 patients (200 major trauma cases and 500 non-major trauma cases) per network. This should be a manageable work load for research paramedics (approximately 9 cases to code per working day), while providing sufficient statistical power.

Statistical analyses

Full details of planned analyses will be contained in a specific statistical analysis plan (SAP), which will conform to Sheffield CTRU SOP ST001. Sample derivation and data linkages will be presented with a STROBE flow diagram.

The Phase Two validation study will be conducted, reported and presented according to the latest STARD 2015 guidelines for diagnostic accuracy studies.[37, 38] Under-triage is defined as the proportion of patients who could benefit from specialist care not transported to a

MATTS Study

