6.1 Service Evaluation Study

The Phase 3 Service Evaluation will assess the real-life operational performance of the candidate triage tool, selected at the end of Phase Two, based on actual transport destinations.

Study setting and population

In Phase Three the most optimally performing candidate triage tool, determined from Phase Two, will be voluntarily implemented operationally in a major trauma network within each ambulance service. System-level accuracy, compliance, and usability will be evaluated. Consecutive patients of any age will be included if attended by EMS following injury over the 6 month study period. Patients transported to participating trauma networks from non-study EMS, transported to out-of-area hospitals, or where record linkage would not be possible will again be excluded. Patients from mass-casualty major incidents will again be excluded.

Implementation of the candidate triage tool

Introduction of the candidate triage tool will be conducted in partnership with participating trauma networks. Training will be provided to all relevant ambulance service staff using standard methods for implementing protocol changes within ambulance services (e.g. face-to-face sessions or on-line teaching packages). Major Trauma Centres and Trauma Units will be informed of changes to pre-hospital triage tools in advance.

Identification of injured patients and data collection

EMS and hospital data collection will be performed as described for Phase Two.

Data linkage, handling and record keeping

Data linkage, data handling and record keeping will be performed as described for Phase Two.

Consent procedures

In Phase Three an optimal candidate trauma triage tool will be selected by trauma networks for implementation. A service evaluation will subsequently be performed using routinely collected data to evaluate real life performance and compliance. As no additional data will be collected, and the triage tool will be applied to all patients presenting with injury, we will not obtain individual patient consent, but we will seek ethical approval from an NHS research ethics committee and CAG to analyse anonymised linked data.

Sample size calculation

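### Section 5.1 samples the whole LAS cohort, cases included, against the case census behind the 800; and the Summary and section 5.1 define the non-case frame differently, the Summary's using a Phase Three outcome

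*Protocol*

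**What the plan says.** **Sampling.** The Scientific Summary describes Phase Two as a diagnostic accuracy cohort "with a census sample of reference standard positive major trauma cases; and random sample of reference standard negative cases without major trauma", without excepting any network. The sample size paragraph of section 5.1 builds on this. It takes "approximately 200 major trauma cases (ISS>15) per 4 months per trauma network", sums to 800 positives, adds 2,000 coded negatives (a 2% fraction), and arrives at about "700 patients (200 major trauma cases and 500 non-major trauma cases) per network".

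The population paragraph of the same section says something else. For three services, "A census sample of consecutive patients will be enrolled over 4 months from WMAS, YAS, and SWAST in Phase Two". For London, because its records are on paper, "a representative cohort will be enrolled from the participating LAS Major Trauma Network using random sampling".

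In Phase Three, section 6.1 states: "Consecutive patients of any age will be included if attended by EMS following injury over the 6 month study period". It has no LAS exception. Its sample size paragraph again codes 3,000 negatives at 2%.

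**Non-case frame.** For the negative sample in both phases, the Summary states: "Appropriate patients identified using injury related working impression codes, use of major trauma interventions, hospital trauma team pre-alerts, and call priority". Section 5.1 finds injured patients another way: "Diagnostic codes for injury will be used where possible, with additional electronic searching of free text filters", with manual review of unclear records. Section 6.1 refers back to Phase Two for identification and data collection. The Summary also bases the Phase Three outcome on actual destination and observed pre-alerts.

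**The concern.** A census of cases and a random sample of the whole cohort are different designs, and the LAS sentence asks for the second where the sample size assumes the first. A site team following section 5.1 literally would abstract only some of the London cases. Cases never abstracted cannot be recovered at analysis, and if the fraction is not recorded they cannot be weighted either. Section 5.1 also promises to study tool performance across differing settings, which needs enough cases from London.

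The frame matters for a different reason. Cases are found through TARN whatever the crew did. If non-cases enter partly because a pre-alert was made, and pre-alerts are part of what Phase Three measures, the denominator of over-triage depends on its numerator. In Phase Two the link is only indirect: the primary analysis scores tools from recorded ambulance data regardless of destination, although paramedic judgement is one of the index tests.

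**Working it through.** **Inputs from the protocol:** 200 cases and 25,000 injured patients per network over 4 months; four networks; target sensitivity 95% and specificity 70%; 2,000 coded negatives at 2%. **Assumed:** the LAS fraction f, which the protocol does not give.

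**1. Reproducing the plan.** Half-width = 1.96 × √(p(1−p)/n).
- 800 cases at 95%: 1.96 × √(0.0475/800) = 1.51 points, which rounds to the stated 2%. The precision table's 811 for ±1.5 points also reproduces.
- 2,000 negatives at 70%: 1.96 × √(0.21/2,000) = 2.01 points, as stated.
- 2% of the 99,200 negatives (100,000 − 800) = 1,984, about 2,000.

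The plan's figures are therefore consistent with the census and 2% design, and 800 is reached only with all 200 LAS cases.

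**2. Following the LAS sentence.** Total cases = 3 × 200 + 200f = 600 + 200f. If LAS cases are weighted by 1/f to represent their network, the effective number is (600 + 200)² / (600 + 200/f).

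| f (assumed) | LAS cases | Total | LAS share of cases | Half-width, unweighted | Effective n, weighted | Half-width, weighted |
|---|---|---|---|---|---|---|
| 1 | 200 | 800 | 25% | 1.51 | 800 | 1.51 |
| 0.5 | 100 | 700 | 14.3% | 1.61 | 640 | 1.69 |
| 0.25 | 50 | 650 | 7.7% | 1.68 | 457 | 2.00 |
| 0.02 | 4 | 604 | 0.7% | 1.74 | 60 | 5.50 |

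The unweighted interval looks little changed because the pooled estimate then largely leaves London out: 200f/(600 + 200f) of cases instead of a quarter. Restoring London's share by weighting is what costs precision.

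**3. The other three services.** Consecutive enrolment covers 3 × 25,000 = 75,000 records against 2,800 planned for coding across all four networks. In Phase Three it covers 150,000 against 1,200 + 3,000 = 4,200. These agree only if the consecutive cohort is the source population and coding applies to all cases plus a sample of negatives. The population paragraphs do not say so.

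**4. The frames side by side.**
- Summary, both phases: working impression codes, trauma interventions, pre-alerts, call priority.
- Section 5.1, adopted by 6.1: injury codes, free text filters, manual review.
- Phase Three outcome in the Summary: destination and pre-alert.

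Pre-alert is thus both an entry criterion and an outcome. Its effect depends on whether meeting any one of the four criteria is enough or several are needed, and on how many patients enter by pre-alert alone. The protocol gives neither, so no bias figure can be derived.

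**The case against.** The design intent is clear inside section 5.1 itself: the sample size paragraph states 200 cases and 500 non-cases for every network. On that view the LAS sentence is an unaligned remnant and no one would apply it to cases. Even at f = 0.02 the unweighted half-width of 1.74 points still rounds to the stated 2%, and a separate London estimate is neither an objective nor a listed subgroup. This limits the effect on pooled precision. It does not remove the conflict, because the sentence is current text, sets LAS apart from the services with a census, and does not confine the sampling to negatives.

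Several stronger readings are tempting and are not supported:
- *Nearly all London cases would be lost.* The 2% belongs to the coding of negatives. The LAS fraction is not stated, so the f = 0.02 row is only the low end of an assumed range.
- *The three-service census makes coding unworkable.* Enrolment can be read as forming the source cohort electronically, with 2% of negatives then coded. This needs a clarifying sentence, not a redesign.
- *Sections 5.1 and 6.1 use different frames, or both sample LAS.* LAS sampling appears only in 5.1, and 6.1 adopts the 5.1 process. The frames differ between the Summary and 5.1.
- *The Summary's frame admits uncoded non-cases only if they are triage-positive, or multiplies over-triage.* Pre-alert is one of four criteria, and call priority and interventions are not triage-tool results. Any number would need invented inputs.

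It is also fair to say that dropping pre-alerts and interventions outright could miss injured, over-triaged patients who carry no injury code. The fix allows for that.

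**Conclusion.** The point stands as a conflict between current parts of the protocol. Random sampling of the whole LAS cohort cannot be carried out together with a census of cases or with the 200 LAS cases counted in the 800. Its size depends on the unstated f. Over the assumed range of 0.5 to 0.02, the half-width for 95% sensitivity is 1.61 to 1.74 points unweighted, or 1.69 to 5.50 points weighted, against 1.51. London would be left with 100 to 4 cases for the comparison across settings. These figures assume equal networks of 200 cases and a simple normal-approximation interval.

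The frame conflict is also real. In Phase Three, choosing non-cases partly on pre-alerts puts specificity and over-triage at risk of bias of unknown size. In Phase Two the risk is indirect.

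**What to change.** Amend the population paragraphs of sections 5.1 and 6.1 to say that:
- consecutive injured patients form the source cohort in all four networks, LAS included;
- every reference-positive case is taken and coded;
- negatives are coded from a random sample at a common 2% fraction, about 500 per network in Phase Two (2,000/4) and 750 in Phase Three (3,000/4). Record the fractions achieved and weight the pooled estimates if they differ between networks.

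Use one non-case frame in the Summary, 5.1 and 6.1, defined by evidence of injury that does not depend on the triage result: injury codes, dispatch records and free text. If pre-alerts or interventions are kept to find injured patients without a code, make them separate strata with recorded sampling fractions and analyse with weights.

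The cost is amendment wording and, if strata are used, a weighted analysis. No stated sample size changes, and the LAS workload of about 700 records is already in the plan. The change has to precede sampling, since cases not abstracted and fractions not recorded cannot be repaired later.

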Data linkage between a) MATTS major trauma cases collected by TARN, and b) EMS identified patients with injuries and will initially be conducted deterministically based on ambulance service unique identifiers (e.g. incident, CAD and call sign numbers), tailored to the context of each ambulance service. In cases where deterministic record linkage is not possible, a probabilistic TARN algorithm based on patient demographics, hospital destination, and incident date/time will be used. Unmatched major trauma cases where a confident match is not possible will be examined by hand and if a confident match cannot be made will be excluded. Matched major trauma patients will represent triage tool true positives and true negative cases. Data linkage will be performed without direct patient identifiers e.g. name, date of birth, address, and any indirect patient identifiers will be removed from the data set after successful linkage has taken place.

Any included EMS identified patients with injuries who are not identified as having major trauma, will be classified as reference standard negative, and will therefore not undergo any data linkage. These patients will represent false positive and true negative cases. We will

perform a detailed case note review by hand for a random sample of these cases to ensure we are not missing a significant number of major trauma cases.

Data handling and record keeping

The collaborating Ambulance Services and TARN will both check their data for any patients who have registered for the NHS 'National data opt-out', and remove any patients as necessary before the transfer of data. Non-identifiable EMS and TARN data will then be transferred to the University of Sheffield by secure NHS/University email accounts using encrypted, password protected, data files.

This information will then be entered into a secure University of Sheffield database. The CTRU, Study Manager, research assistant and the Data Management Team will work with research paramedics to ensure the quality of data provided. Validation reports will be run regularly to check the study data for completeness, accuracy and consistency. Discrepancies will be generated and managed to resolution. Data monitoring and audit will be conducted in accordance with the University of Sheffield CTRU SOP QU001 and DM009.

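### The linkage rule can drop major trauma cases whose ambulance record was not flagged as injury, so sensitivity may be overstated; the same paragraph also mislabels false negatives as true negatives

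*Protocol*

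**What the plan says.** **Labels.** Protocol section 5.1, Data linkage, states: "Matched major trauma patients will represent triage tool true positives and true negative cases". The next paragraph says of injured patients not identified as major trauma: "These patients will represent false positive and true negative cases".

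**Linkage in section 5.1.** TARN major trauma cases are linked to injured patients identified by the ambulance service. Linkage is first deterministic on ambulance identifiers, then probabilistic. Cases still unmatched "will be examined by hand and if a confident match cannot be made will be excluded". The exclusions under Setting and study population end in the same way: "or where record linkage would not be possible will be excluded". The ambulance set is built under Identification of injured patients, from diagnostic codes and free-text filters, with manual review of equivocal records.

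**Linkage in the Scientific Summary (Phase Two).** The rule is worded differently: "Research paramedics to review all reference standard positive cases and manually determine a definitive EMS identifier for deterministic linkage". It is followed by: "Non-linked cases assumed to be reference standard negative".

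Section 6.1 applies the Phase Two linkage to Phase Three unchanged.

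**The concern.** The label assigns true negatives to both reference groups and false negatives to neither, in the paragraph that tells the data team how to fill the two-by-two table.

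The exclusion matters more. Tools are scored from the ambulance record, and whether that record can be matched depends on whether it was identified as injury. If a crew did not recognise or record an injury, the record may fall outside the filter. The TARN case then has nothing to match to and is excluded. Such a record is also one on which a triage tool could well score negative. Being dropped would then be related to the tool result, and the loss would fall on the sensitivity denominator.

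At stake are sensitivity and under-triage, on which the candidate tool is largely chosen. In Phase Three, section 2 says that paramedic recognition of patients eligible for triage will be observed. Excluding unrecognised cases would weaken that measure.

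The two linkage rules also differ on what happens to a non-linked case: excluded in section 5.1, assumed negative in the Scientific Summary.

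**Working it through.** **Inputs.** From section 5.1, Sample size calculation: 800 reference-positive cases, target sensitivity 95%; 2,000 reference-negative cases, a 2% sample, target specificity 70%. Not given, so assumed: the unlinked share *u* and the sensitivity *s* among unlinked cases.

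**Step 1: the plan's precision.** Half-width = 1.96 × √(p(1−p)/n).
- Sensitivity: 1.96 × √(0.95 × 0.05 / 800) = 1.51 points. The text gives 2%, which agrees after rounding. The Scientific Summary table gives 811 cases for ±1.5 points, and 1.96² × 0.95 × 0.05 / 0.015² = 811.
- Specificity: 1.96 × √(0.70 × 0.30 / 2000) = 2.01 points, against a stated 2%.

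**Step 2: the label.** At the target values, true positives are 0.95 × 800 = 760, false negatives 40, true negatives 0.70 × 2,000 = 1,400 and false positives 600.

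| Reading | Sensitivity | Specificity |
|---|---|---|
| Standard definitions | 760/800 = 95.0% | 1400/2000 = 70.0% |
| Label taken literally (40 moved to true negatives) | 760/760 = 100% | 1440/2040 = 70.6% |

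On the literal reading every tool would have zero under-triage. That cannot be meant. Statistical analyses in section 5.1 equates under-triage with 1 minus sensitivity, the Scientific Summary tabulates sensitivities from 0.50 to 0.97, and sections 4.3 and 6.1 name false negatives.

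**Step 3: bounds from the exclusion.** With 95% sensitivity in linked cases:
- all unlinked cases missed: (1 − u) × 0.95
- all unlinked cases detected: (1 − u) × 0.95 + u

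| u (assumed) | All missed | All detected | Change from 95% |
|---|---|---|---|
| 5% | 0.95 × 0.95 = 90.25% | 95.25% | −4.75 to +0.25 points |
| 10% | 0.90 × 0.95 = 85.5% | 95.5% | −9.5 to +0.5 points |

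**Step 4: direction.** Suppose true sensitivity over all eligible cases is 95%. The value observed in linked cases is (0.95 − u × s)/(1 − u).

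| s (assumed) | u = 5% | u = 10% |
|---|---|---|
| 65% | 96.6% | 98.3% |
| 85% | 95.5% | 96.1% |
| 95% | 95.0% | 95.0% |
| 100% | 94.7% | 94.4% |

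Sensitivity is overstated if unlinked cases are detected less often than linked ones, unaffected if equally often, and understated if more often.

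**Step 5: specificity.** If 10% of 800 positives (80) were unlinked and all their records sat in the negative sampling pool, a 2% sample would pick up about 80 × 0.02 = 1.6 of 2,000, or 0.08 points. The issue is confined in practice to sensitivity.

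**The case against.** A reader might infer that the table has no false-negative cell and that sensitivity is inflated as a result. The documents do not support this. Every definition and table that bears on sensitivity requires the cell, and matched patients with a negative tool result remain in the data. The label is a slip, not an analysis rule.

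A reader might also infer that the exclusion is certain to overstate sensitivity. That is not established either. A case with no ambulance record has no index test result, exclusion comes only after three attempts at linkage, and step 4 shows that the error can go either way. Nor is it safe to argue that cases at non-specialist hospitals lack an ambulance number: ambulance identifiers are a mandatory core field in TARN, and the protocol's worry about those hospitals concerns case ascertainment. The primary analysis also scores tools regardless of destination.

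The protocol has safeguards. The injury search uses free text as well as codes, a sub-sample of unfiltered records is read by hand, a random sample of negatives has case-note review, and linkages appear in a flow diagram. The Scientific Summary lists injury-code criteria only under negatives, so its rule for positives may already reach beyond the filter. Its sentence on non-linked cases may refer only to ambulance records without a TARN match.

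What remains is narrower. The unfiltered sub-sample measures how many cases are missed, but the text does not say they are added back. The case-note review covers only records already in the injury set. The flow diagram gives counts, not bounds. The missing-data analyses are not said to cover excluded cases. The route through the injury filter does not depend on destination, so scoring regardless of destination does not answer it. Both the exclusion and the conflict between the two linkage rules are fixed in the protocol itself, so they are not matters left to the SAP.

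**Conclusion.** There are two findings of different weight.

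1. The label is a definite but minor wording error with no effect on the estimates as the protocol defines them.
2. The linkage rule is a moderate problem. Sections that should agree give different rules, and section 5.1 as written lets major trauma outside the injury filter leave the sensitivity denominator for a reason plausibly tied to a negative tool result. Sensitivity may be overstated.

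The size is unknown, because it rests on two quantities that the protocol does not give. The bounds in step 3 are illustrations that take 95% in linked cases and assume 5% or 10% unlinked. They are lopsided: at 10%, counting all unlinked cases as missed moves the estimate by 9.5 points and counting all as detected by 0.5, against a half-width of about 1.5. At a high sensitivity, even a modest unlinked share could therefore matter more than sampling error. If linkage failure is unrelated to the tool result, there is no bias.

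**What to change.** - In section 5.1, Data linkage, change the label for matched major trauma patients to true positives and false negatives.
- State one linkage rule in the Scientific Summary and section 5.1: manual identification of the ambulance record for each positive case, not limited to the injury-filtered set. Keep matches found outside the filter in the sensitivity denominator.
- State that treating non-linked cases as reference negative applies only to ambulance records without a TARN match.
- Report the number of otherwise eligible positives that remain unmatched, and give sensitivity with all of them counted as missed and then as detected, in Phase Two and Phase Three.

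The cost is an amendment to the wording and some extra look-up. Section 1 puts injury at about 20% of ambulance responses nationally, so screening every record could mean about five times the volume (1/0.20). The proposal avoids this, because the search starts from the few positive cases that do not match within the filter. The sponsor should check that the existing approvals cover looking outside the injury set. The reported range for sensitivity will be wider.
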